5.1.3 Escalation Regimen

All patients will receive treatment with single-agent tebentafusp on C1D1 and C1D8 at 20 mcg and 30 mcg per week, respectively. The majority of moderate-to-severe toxicity associated with tebentafusp is observed at these 2 dose time points and has typically included hypotension, rash, pruritus, fever, and chills. After this initial dosing period, beginning at C1D15 and beyond, patients will receive the escalated dose of 68 mcg. This escalated dose administered at C1D15 will be the dose used for the remainder of the treatment period. Beginning with C1D8, tebentafusp will be administered on the scheduled day (\pm 2 days), and consecutive infusions of tebentafusp must be administered at least 5 days apart.

For the first six patients treated, this intra-patient escalation regimen requires overnight hospitalization and a minimum of pre-dose and Q4-hour vital signs monitoring after the first administration of tebentafusp (C1D1), after the second administration (C1D8), and after the escalated dose of tebentafusp on C1D15 is administered. For the first 3 administrations of tebentafusp, patients should be monitored for at least 16 hours after dosing. “Inpatient hospitalization” refers to a facility with fully functional resuscitation facilities, 24-hour monitoring, and physician availability. See Section 10.4 for additional details on vital signs monitoring.

Inpatient monitoring at C2D1 will be determined by the toxicity observed in the C1D1–C1D15 doses as follows:

1. If the escalated dose at C1D15, administered as an inpatient, does not raise safety concerns (and the patient does not experience an adverse reaction involving hypotension of grade \geq 2), the subsequent dose at C2D1 and all subsequent doses can be administered on an outpatient basis.

2. If the patient experiences hypotension requiring any medical intervention (National Cancer Institute Common Terminology Criteria for Adverse Events [NCI CTCAE] grade ≥ 2) at C1D15, then the C2D1 dose should be administered with inpatient monitoring, similar to C1D1–C1D15. If the patient does not experience hypotension requiring medical intervention at the C2D1 dose administered as an inpatient, then all subsequent doses can be administered on an outpatient basis.

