3. Hospitalization at other days (eg, Cycle 2 and beyond) is determined at the discretion of the principal investigator based on the patient's history and tolerance for the initial doses of the study medication, with the exception of patients experiencing a treatment delay (please refer to bullet 4 below).
4. Patients experiencing a break or delay in treatment for any reason of more than 2 weeks AND with a history of a grade 3 or 4 event of hypotension with tebentafusp dosing during the first weeks of treatment will be monitored as an inpatient for the dose subsequent to the break in dosing, regardless of the timing of the break in dosing, with vital signs monitored at a minimum of every 4 hours and monitoring for at least 16 hours after dosing.

If none of the first six patients experience **Grade ≥ 2 CRS or Grade ≥ 3 infusion-reactions**, subsequent patients can be treated as an outpatient for their intra-patient dose escalation. However, all patients undergoing intra-patient dose escalation require monitoring in a facility with access to resuscitation equipment, rescue medications, and physician availability. Patients must be monitored for at least 8 hours post-end of infusion on C1D1, C1D8, and C1D15. Vital signs must be confirmed stable prior to discharge. Minimum thresholds are body temperature $< 38.2^{\circ}\text{C}$, heart rate < 110 beats per minute, and oxygen saturation 92% on room air.

Antihypertensive drugs are allowed as concomitant medications; however, because transient hypotension has occurred during infusions of monoclonal antibodies and ImmTACs, the investigators should consider reducing or not administering antihypertensives for 24 hours before and after the tebentafusp administration during at least the first 3 weeks of treatment. Appropriate management of patients, especially those with more severe hypertension, receiving medications that may cause rebound hypertension when abruptly discontinued or those who are on multiple blood pressure medications should be discussed with a cardiology consultant and the Principal Investigator.

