10.5 VITAL SIGNS

Vital signs (body temperature, pulse rate, respiratory rate, and blood pressure, oxygen saturation) must be performed before dosing, and after the tebentafusp administration as indicated in Table 3 and as per institutional standards.

Vital signs should be assessed on the scheduled day, even if study treatment is being withheld. More frequent examinations may be performed at the discretion of the investigator if medically indicated and will be recorded as unscheduled assessment.

Table 2 Tebentafusp Post-dose Vital Signs Monitoring

C1D1, C1D8, C1D15 Inpatient monitoring required for all	Vital signs monitored per institutional standards at a minimum of every 4 hours.
--	--

dosings of the first six patients; if no Grade \geq 2 CRS or Grade \geq 3 infusion-reactions are seen among the first six patients, subsequent patients can be treated as outpatients
	
Patients should be monitored for at least 16 hours after dosing. Patients experiencing grade 2 or greater hypotension at C1D15 require inpatient monitoring for the subsequent/next C2D1 dose. Those experiencing grade 3 or 4 hypotension at C1D1, C1D8, or C1D15 require hourly vital signs monitoring for a minimum of 8 hours after dosing for any doses administered as an outpatient through C3D1. Patients who are permitted to receive dose escalation treatment as an outpatient must be monitored for at least 8 hours post-end of infusion on C1D1, C1D8, and C1D15. Vital signs must be confirmed stable prior to discharge. Minimum thresholds are body temperature $<$ 38.0°C, heart rate $<$ 100 beats per minute, and oxygen saturation \geq 92% on room air. Patients should be informed to reside within a 30-minute travel distance to a local emergency room. Patients will be provided a wallet card indicating their current treatment status at the time of discharge.

C2D1 Inpatient monitoring required for exception noted
	
Patients experiencing a grade 2 or greater hypotension at C1D15 must be observed as an inpatient for C2D1 dose, with vital signs performed at a minimum of every 4 hours and monitoring for at least 16 hours after dosing.

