APPENDIX B

Tebentafusp Toxicity Management Guidelines

Tebentafusp Toxicity Management Guidelines	
Worst Toxicity	Recommended Dose Modifications
Pruritus (graded per CTCAE v5.0)	
Grade 1	Continue dosing. If symptomatic, consider a systemic antihistamine regimen (see Grade 2 guidance below).
Grade 2	
May continue dosing. Intrapatient escalation is contraindicated if symptoms have not improved to Grade ≤ 1 prior to dosing. Treat according to institutional practice and/or implement the guidance described below. Use systemic management and/or local skin management as indicated by symptoms. With bullous formation or blistering rashes consider a dermatology consultation to rule out other causes (eg, bullous pemphigoid). Oral or topical corticosteroids can be used. If bullous formation or blistering recur, consult the Medical Monitor for guidance.
 
Antipruritic regimen:
 
A systemic antihistamine regimen is recommended as first-line management of pruritus, eg, nonsedating, long-acting antihistamine (cetirizine, 10 mg oral or equivalent). If a sedating antihistamine is preferred (eg, evening dosing), consider diphenhydramine 25 mg oral or intravenous (IV). The use of sedating antihistamines should be minimized in participants with comorbid pulmonary pathology including pulmonary metastases or underlying inflammatory airways disease such as chronic obstructive pulmonary disease or asthma.
 
Topical corticosteroid regimens
 
Preparation of recommended regimens is as follows:
 
 For the face and/or intertriginous areas (including genitalia), alclometasone 0.05% or hydrocortisone 2.5% creams are recommended. For other body areas (ie, the trunk and extremities), clobetasol or betamethasone 0.05% creams are recommended. Consider a spray preparation for ease of application on the trunk. For scalp involvement, consider a foam preparation. 
NOTE: Montelukast (10 mg orally) may be considered as an adjunctive therapy in participants with persistent symptoms despite antihistamine and topical corticosteroid therapy.
 
Prophylaxis for subsequent doses is generally not required after Grade 2 pruritus, but a nonsedating antihistamine may be considered, especially for recurrent or persistent symptoms.

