Grade 3	
Hold all doses of tebentafusp until improvement to CTCAE Grade \leq 1.
 
 If Grade 3 rash resolves to \leq Grade 1 in < 7 days, 
 If at 20 or 30 mcg dose, stay at this dose level. Resume escalation once the current dose level is tolerated. If at 68 mcg, treatment may continue at the current dose level. If Grade 3 rash resolves to \leq Grade 1 in 7 to 21 days, 
 If at 20 or 30 mcg dose, stay at this dose level. Resume escalation once the current dose level is tolerated. If at 68 mcg, treatment may continue at the current dose level. Corticosteroid prophylaxis is required for at least the next 3 doses If Grade 3 rash does not resolve within 21 days, permanently discontinue all study interventions. 
Manage rash according to the institutional protocol and guidance below.
 
Management:
 
Treat according to institutional practice, which generally includes an antipruritic regimen (see Grade 2 management above). In addition, corticosteroid treatment (systemic) can be considered for symptomatic rash that does not respond to antihistamine, topical corticosteroid, or montelukast therapy (recommend oral prednisone 20–40 mg, a single dose of 125 mg hydrocortisone intravenous, or the equivalent for refractory rash). For recommended systemic or topical regimens, refer to Grade 2 management above.
 
Prophylaxis:

	
In participants experiencing Grade 3 rash, administration of a nonsedating antihistamine prophylaxis dose is recommended for the subsequent dose of tebentafusp, approximately 1–2 hours prior to the tebentafusp dose being administered (eg, cetirizine 10 mg or equivalent).
 
Prophylaxis with corticosteroid should be considered if rash recurs at a similar or worse severity despite antihistamine prophylaxis and is required if any episode does not resolve in < 7 days (recommend oral prednisone 20–40 mg, a single dose of 125 mg hydrocortisone intravenous, or the equivalent). If steroid prophylaxis is used, the steroid dose should be titrated to the minimum effective dose and ultimately discontinued if possible.

Grade 4	
Permanently discontinue tebentafusp.
 
As above for Grade 3 except administer intravenous corticosteroid (eg, 2 mg/kg methylprednisolone or equivalent); additionally, consultation with a dermatologist is recommended.

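### A dose repeat required by Appendix B moves the first 68 mcg dose outside the 16-hour and 8-hour monitoring rules; without qualifying Cycle 1 hypotension, the stated minimum is then 1 hour

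*Protocol*

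**What the plan says.** **Repeating a dose.** For Grade 3 rash and Grade 3 pruritus, Appendix B holds dosing until recovery to Grade 1 or lower. It then states: "If at 20 or 30 mcg dose, stay at this dose level. Resume escalation once the current dose level is tolerated". For Grade 2 pruritus, dosing may go on, but "Intrapatient escalation is contraindicated if symptoms have not improved to Grade" 1 or lower; a repeat is possible there but not required. Section 6 accepts that either escalation step may be postponed.

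**Long observation.** Section 5.1.3 says: "For the first 3 administrations of tebentafusp, patients should be monitored for at least 16 hours after dosing". Section 5 has the same rule, and Table 2 (Section 10.5) attaches it to C1D1, C1D8 and C1D15. Where outpatient escalation has been allowed, Section 5.1.3 says: "Patients must be monitored for at least 8 hours post-end of infusion on C1D1, C1D8, and C1D15".

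**C2D1 and later.** Section 5.1.3 begins "Inpatient monitoring at C2D1 will be determined by the toxicity observed in the" C1D1 to C1D15 doses, and calendar footnote 3 says the same. Item 1 opens "If the escalated dose at C1D15, administered as an inpatient, does not raise safety concerns" and, on that condition, releases the patient to outpatient dosing from C2D1. Item 3 reads: "Hospitalization at other days (eg, Cycle 2 and beyond) is determined at the discretion of the principal investigator".

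**Table 2 after Cycle 1.** On hypotension: "Patients experiencing grade 2 or greater hypotension at C1D15 require inpatient monitoring for the subsequent/next C2D1 dose", with 16 hours of monitoring. Grade 3–4 hypotension at any Cycle 1 dose brings 8 hours of hourly vital signs for outpatient doses through C3D1. Patients with neither need 1 hour in clinic.

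**The concern.** The monitoring rules assume that 68 mcg is first given at C1D15 as the third administration. Appendix B can break that assumption, because monitoring follows the visit day or the dose count while first exposure to full dose can move later.

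On the normal schedule the first 68 mcg dose carries a mandatory 16 hours of observation (8 if outpatient). A patient who has just had a Grade 3 skin reaction at a lower dose, and so repeats it, could receive that same first full dose with 1 hour. Section 7.3.1 reports that fever was present in nearly all CRS cases and generally arose within 8 to 10 hours of infusion, so a 1-hour stay can end before it. The hypotension trigger has the same weakness: it looks at C1D15, which for this patient is a 20 or 30 mcg dose.

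**Working it through.** **1. Where the first 68 mcg dose falls.** Inputs: weekly dosing of 20, 30, then 68 mcg in 21-day cycles (Section 5.1.3, Table 1) and r on-schedule repeats of 20 or 30 mcg in total. The first 68 mcg dose is administration 3 + r, on day 1 + 7(2 + r).

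| r | Sequence (mcg) | Administration | Day | Visit | Dose at C1D15 |
|---|---|---|---|---|---|
| 0 | 20-30-68 | 3 | 15 | C1D15 | 68 |
| 1 | 20-20-30-68 or 20-30-30-68 | 4 | 22 | C2D1 | 30 |
| 2 | 20-20-20-30-68, 20-20-30-30-68 or 20-30-30-30-68 | 5 | 29 | C2D8 | 20 or 30 |

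The r = 0 row reproduces the protocol's own schedule.

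**2. Which rules reach it when r = 1.**

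- 16 hours, first three administrations: no, it is the fourth.
- 16 or 8 hours at C1D1, C1D8 and C1D15: no, it is C2D1.
- Section 5.1.3 item 1: its condition is a tolerated inpatient escalated dose, which has not yet been given. Read for its purpose, this points to inpatient dosing.
- Section 5.1.3's C2D1 rule and footnote 3: they look to toxicity at C1D1 to C1D15, here only 20 and 30 mcg doses.
- Section 5.1.3 item 3: discretion.
- Table 2 hypotension rows: 16 hours inpatient at C2D1 after Grade 2 or greater hypotension at C1D15; 8 hours for outpatient doses after Grade 3–4 hypotension in Cycle 1.
- Table 2 row for Cycle 2 and later, with neither kind of hypotension: 1 hour. This row does not ask whether 68 mcg has already been tolerated.

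**3. How many patients.** Section 7.3.2 gives Grade 3 acute skin reactions in 20.4% of monotherapy patients, pooled over all studies. For 23 treated patients, 0.204 × 23 = 4.69. This is a ceiling at that rate, because it counts events at every dose, edema and erythema as well as rash and pruritus, and patients with qualifying hypotension. The share arising at 20 or 30 mcg is not given. Assumed shares of 10%, one third and 100% give 0.47, 1.56 and 4.69 patients. The Grade 2 pruritus route cannot be estimated. Grade 3 CRS at 20 or 30 mcg also forces a repeat; at 0.8% (Section 7.3.1) it adds at most 0.008 × 23 = 0.18 patients.

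**4. Whether the comparator is 16 or 8 hours.** Outpatient escalation opens only if none of the first six patients has Grade 2 or higher CRS or a Grade 3 or higher infusion reaction. Section 7.3.1 reports Grade 2 CRS in 76% and Grade 3 in 0.8% in the largest dataset. If those uveal melanoma rates carried over (an assumption), the chance of no such CRS in six is (1 − 0.76 − 0.008)^6 = 0.232^6, about 0.0002. Sixteen hours is the likelier comparator.

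**The case against.** **Assessments move with infusions.** Section 5 shifts study assessments when an infusion is delayed or moved off its day, and Section 6 describes a postponed step as a delay. With item 1 of Section 5.1.3, a site could fairly take the C1D15 monitoring to travel with the 68 mcg dose. This stands to the extent that the text is ambiguous. It does not close the gap: a repeat given on its scheduled day moves no infusion, and no shift of visit labels can turn a fourth administration into one of the first three.

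**Early doses carry most toxicity.** Sections 5 and 5.1.3 say that most moderate-to-severe toxicity comes at C1D1 and C1D8. Section 7.3.1 reports that CRS becomes rarer and milder over the first three infusions. An affected patient has had an extra low dose and must tolerate it before escalating. This also stands, and it is why no added risk can be claimed as shown. Yet the protocol still mandates long observation of the first 68 mcg dose on the normal schedule and gives no reason for less after a repeat.

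**Other safeguards.** Section 5.1.3 requires a facility with resuscitation equipment, rescue medication and a physician for everyone undergoing escalation, without setting a duration. Hospitalisation remains possible at discretion. Appendix B requires corticosteroid premedication at the next dose after Grade 2 CRS, and steroid prophylaxis for at least three doses when a Grade 3 skin event takes 7 to 21 days to resolve; after one repeat, that covers the first 68 mcg dose. These reduce the exposure but set no observation time.

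A reader might infer that 1 hour is Table 2's only minimum after any repeat. It is not: the hypotension rows set 16 and 8 hours. A reader might also try to count patients left with neither long monitoring nor steroid cover. The protocol does not support such a count, because it gives no per-dose rates of Grade 2 CRS and no resolution times specific to Grade 3 skin events.

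**Conclusion.** The point holds for patients without qualifying Cycle 1 hypotension. After a repeat required for Grade 3 rash or pruritus, no mandatory 16-hour or 8-hour rule covers the first 68 mcg dose. The provisions on C2D1 point in different directions, and a site following Table 2 could observe for 1 hour.

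The gap is narrow: at most about 4.7 of 23 patients by the Grade 3 skin route if the pooled rate applies to this population, and probably fewer. The added risk cannot be quantified from the protocol. Endpoint, sample size and analysis are unaffected. This is a cheap improvement to safety monitoring; the documents do not show that patients would be harmed as the text stands.

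**What to change.** Amend three places: Section 5.1.3, Table 2 and calendar footnote 3.

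- Apply the 16-hour (or 8-hour outpatient) monitoring to the first three administrations and also to the first 68 mcg dose if it falls later.
- Keep the C1D15 hypotension trigger. After two repeats it still protects C2D1, which is then a 30 mcg dose.
- Add the same trigger for the first 68 mcg dose: Grade 2 or greater hypotension there requires inpatient monitoring of the next dose.

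Tying observation to dose level is already used in Appendix B, which asks for at least 16 hours at the next 68 mcg dose after Grade 2 or 3 CRS at that level. The cost is a wording amendment and one longer stay per affected patient, possibly a second if hypotension occurs.

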5.3 Duration of Therapy

Treatment may continue until one of the following criteria applies:

- Disease progression as defined by RECIST v 1.1 unless criteria for treatment beyond initial PD is met (see Section 5.3.1)
- If continuing treatment beyond initial PD, then patients must discontinue study treatment once further PD warranting treatment discontinuation is met (see Section 5.3.1)
- Initiation of alternative anti-cancer therapy including another investigational agent
- Unacceptable toxicity as defined in Appendix B or any AE that, in the opinion of the investigator, contraindicates further dosing
- Withdrawal of consent from further treatment with investigational product by the patient or the investigator
- Patient is lost to follow-up
- Patient is determined to have met 1 or more of the exclusion criteria or failed to meet all of the inclusion criteria for study participation AND continuing to receive investigational product might constitute a safety risk. Patients who fall into this category and for whom continuation of treatment is not thought to pose a safety risk, in the opinion of the investigator, may continue to receive study treatment
- Pregnancy or intent to become pregnant

At the time patients discontinue study treatment, the EOT visit should be scheduled in the appropriate window of 14 days after the last dose was administered. At this visit, all of the assessments listed for the EOT visit will be performed. If the decision to withdraw the patient occurs at a regularly scheduled visit, that date of visit may become the EOT visit rather than having the patient return for an additional visit (safety follow-up will still continue for the full 30-day observation period). An EOT disposition document should be completed at the EOT visit, giving the date and reason for stopping the study treatment.

Patients who discontinue study treatment should NOT be considered withdrawn from the study. They should return for the assessments indicated in Section 11. If they fail to return for these assessments for unknown reasons, every effort (eg, telephone, email, and registered letter) should be made to contact them. If a patient discontinues study treatment, but continues study assessments, the patient remains on study until such time as he/she completes protocol criteria for ending study assessments. At that time, the reason for study completion should be documented.

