6. DOSING DELAYS/DOSE MODIFICATIONS

All dose modifications should be based on the worst preceding toxicity. See Appendix B for management of tebentafusp-related AEs.

For tebentafusp, escalation steps during interpatient dose escalation (ie, increasing from 20 mcg to 30 mcg or increasing from 30 mcg to 68 mcg) may be delayed. Dose reductions from 68 mcg are not permitted.

Weekly tebentafusp doses may be omitted as needed for management of AE. After completing 3 months of treatment, the Investigator may permit occasional, infrequent dose omissions to accommodate holidays, vacations, and the like.

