Grade 3	
Management as above (Grade 2) and include the following measures:
 
 Escalate level of care (eg, intensive care unit) as clinically indicated. Maximize immunosuppression with continued high dose IV corticosteroid (eg, methylprednisolone 2 mg/kg/day or equivalent) and/or tocilizumab 8 mg/kg IV (not to exceed 800 mg/infusion) per institutional guidelines. For persistent hypotension, treat with a single vasopressor (with or without vasopressin). 
 Consider adding further immunosuppression measures or additional interventions according to the institutional cytokine release protocol (eg, administer or repeat tocilizumab if not already implemented). Continue to manage symptoms and vigilantly monitor for escalation. For any Grade 3 CRS, restart tebentafusp only after discussion and written approval from the Medical Monitor. 
Once symptoms resolve, at the next dose, do the following:
 
 Administer corticosteroid premedication (eg, dexamethasone 4 to 12 mg or equivalent) at least 30 minutes prior to the next dose If at 20 or 30 mcg dose, stay at this dose level. Resume escalation once the current dose level is tolerated. If at 68 mcg, continue at this dose level; monitor for at least 16 hours post-dose

Grade 4	
Management as above (Grade 3) and include the following measures.
 
 For persistent hypotension, treat with multiple vasopressors (with or without vasopressin). For persistent hypoxia, provide supplemental oxygen using a positive-pressure device. If appropriate, consider additional measures according to the institutional cytokine release protocol. 
Permanently discontinue tebentafusp.

Elevated Liver Enzymes (graded per CTCAE v5.0)	
Grade 2	
 Institute regular monitoring of liver enzymes until improving or resolved. Evaluate concurrent medications for agents that may prolong or exacerbate elevated liver enzymes. Consider IV corticosteroid therapy (eg, methylprednisolone 0.5 to 1 mg/kg/day or the equivalent) if not improving within 72 hours.

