Grade 3 or 4	
Hold all doses of tebentafusp until returned to CTCAE Grade ≤ 1.
 
 Institute regular monitoring of liver enzymes until improving or resolved. Administer intravenous steroids (eg, methylprednisolone 0.5 to 1 mg/kg/day or the equivalent) if no improvement within 24 hours. Consider abdominal imaging and a hepatology consult for persistent elevated liver enzymes, onset of clinical signs or symptoms of liver dysfunction (eg, abdominal pain, nausea, vomiting, jaundice), or impact on liver synthetic function. For any Grade 3 elevated liver enzyme elevation, restart tebentafusp only after discussion and written approval from the Medical Monitor. 
Once elevated liver enzymes improve to NCI CTCAE Grade ≤ 1, if restarting tebentafusp, resume treatment as follows:
 
 If elevated liver enzymes occurred in the setting of Grade 3 CRS, resume at the current dose level. Resume escalation once the current dose level is tolerated. If elevated liver enzymes occurred outside the setting of Grade 3 CRS, then resume intrapatient escalation if the current dose level is less than 68 mcg; otherwise, resume treatment at the current dose level if intrapatient escalation has been completed.
Vomiting (graded per CTCAE v5.0)	
Grade 2	
 Administer antiemetic therapy as per institutional standard. Provide IV fluid support and other supportive measures for additional AEs as needed.
Grade 3 or 4	
 Consider holding all doses of tebentafusp until improvement to NCI CTCAE Grade ≤ 1. Administer antiemetic therapy as per institutional standard. Provide IV fluid support and other supportive measures for additional AEs. Consider instituting antiemetic premedication for at least the next dose (eg, ondansetron 8 mg PO/IV or equivalent).
Other Clinically Significant Adverse Events (graded per CTCAE v5.0)	
Treat according to institutional practice and for potential immune-related AEs of Grade ≥ 3 ; treatment with corticosteroids should be considered. Consult the Medical Monitor for further guidance as needed.	
Grade 3 or 4	
Study medication(s) should be permanently discontinued unless AEs improves to Grade 1 or 0, the Investigator believes the overall benefit-risk favors continued treatment, and there is agreement with the Medical Monitor that the participant may restart treatment at the current or reduced dose.

Confidential

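### Appendix B requires written Medical Monitor approval to restart after a Grade 3 liver-enzyme elevation but states no such control, and no discontinuation, for Grade 4

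*Protocol*

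**What the plan says.** The liver-enzyme section of Appendix B has a Grade 2 row and a combined Grade 3 or 4 row. The combined row holds all doses until Grade 1 or less, sets monitoring, steroid and work-up measures, and then adds the approval step: "For any Grade 3 elevated liver enzyme elevation, restart tebentafusp only after discussion and written approval from the Medical Monitor". The resumption rules that follow apply if tebentafusp is restarted. For an elevation in the setting of Grade 3 CRS, dosing resumes at the current level. For one outside that setting, the row says "then resume intrapatient escalation if the current dose level is less than 68 mcg"; otherwise dosing resumes at the current level. Nothing in these rules separates Grade 4 from Grade 3.

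The CRS section of the same appendix uses a parallel sentence in a row for Grade 3 alone: "For any Grade 3 CRS, restart tebentafusp only after discussion and written approval from the Medical Monitor". Its separate Grade 4 row says "Permanently discontinue tebentafusp".

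The general rules lead back to the same place. Section 5.3 lists as stopping criteria unacceptable toxicity as Appendix B defines it, or "any AE that, in the opinion of the investigator, contraindicates further dosing". Section 6 says "See Appendix B for management of tebentafusp-related AEs".

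**The concern.** Restart controls should not loosen as severity rises. Here the row covers two grades and the approval sentence covers one. A site that follows the text as written must obtain written approval after a Grade 3 elevation. After a Grade 4 elevation that has recovered to the same level, it meets no approval requirement and no instruction to stop. What is at stake is who must agree to re-exposing a patient after the more severe event. No estimate or test is involved.

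**Working it through.** The protocol gives no figure to reproduce. The check is textual, followed by a calculation of how often the case might arise.

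**Step 1. Could naming Grade 3 mean Grade 3 or higher?** Appendix B writes Grade ≥ 3 where it means that, in the row for other clinically significant adverse events. In the combined Grade 3 or 4 row for infusion reactions, Grade 3 alone is singled out for an exception that Grade 4 does not get. So in this appendix Grade 3 means Grade 3.

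**Step 2. Is Grade 4 barred from restart by implication?** Set the Grade 4 rules side by side:

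| Event | Restart rule at Grade 3 | Rule at Grade 4 |
|---|---|---|
| Pruritus | Hold, resume on recovery within 21 days | Permanent discontinuation stated |
| Rash | Hold, resume on recovery within 21 days | Permanent discontinuation stated |
| Infusion reaction | Discontinue, with an exception for early improvement | Permanent discontinuation stated |
| CRS | Written Medical Monitor approval | Permanent discontinuation stated |
| Liver enzymes | Written Medical Monitor approval | Hold to Grade 1 or less; no approval, no discontinuation |

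Where the appendix bars restart at Grade 4 in these sections, it says so. The liver row does not, and its instruction to hold until recovery applies to both grades.

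**Step 3. Does other text supply the approval?**
- Section 5.3 relies on Appendix B or on the investigator's opinion.
- Section 6 relies on Appendix B. It also bases dose modifications on the worst preceding toxicity, so a Grade 4 event that passes through Grade 3 while resolving is not thereby handled as Grade 3.
- The row for other clinically significant adverse events permits restart at Grade 3 or 4 only if, among other conditions, "there is agreement with the Medical Monitor that the participant may restart treatment at the current or reduced dose". By its heading it covers events without a section of their own, and liver enzymes have one. A site might look there, but the row does not govern the case.
- If the liver event occurs with Grade 3 CRS, the CRS row requires approval. With Grade 4 CRS, treatment stops. The gap is therefore confined to Grade 4 elevations outside Grade 3 or 4 CRS.

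**Step 4. How often?** Inputs: 23 treated patients (Section 13.1) and a 1.8% Grade 4 rate across monotherapy studies (Section 7.3.3). The rate is for a grouped term that includes hyperbilirubinemia and hepatic pain, so if it carries over to clear cell sarcoma it is an upper figure for enzyme elevations. Half and double rates show the sensitivity.

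Expected events = 23 × p. Chance of at least one = 1 − (1 − p)^23.

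| Assumed p | Expected events | Chance of at least one |
|---|---|---|
| 0.9% | 23 × 0.009 = 0.21 | 1 − 0.991^23 = 18.8% |
| 1.8% | 23 × 0.018 = 0.41 | 1 − 0.982^23 = 34.1% |
| 3.6% | 23 × 0.036 = 0.83 | 1 − 0.964^23 = 57.0% |

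**Step 5. How many fall outside Grade 3 or 4 CRS?** Section 7.3.1 gives 0.8% Grade 3 CRS and no Grade 4 CRS in study IMCgp100-202, so 23 × 0.008 = 0.18 patients. If all of these also had a Grade 4 liver event, up to 0.184 / 0.414 = 44% of such events would leave the gap at the 1.8% rate. With no overlap, none would. The document does not give the overlap, so this share stays unknown.

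**The case against.** The strongest counter-reading is that only Grade 3 was meant to be restartable. No sentence expressly authorises a Grade 4 restart, the resumption rules are conditional, and Grade 4 means discontinuation for pruritus, rash, infusion reactions and CRS. On that reading Grade 4 is the stricter case. It is weak, because the appendix states discontinuation in each of those sections and the liver row instead holds both grades until recovery. It does bear on the remedy: if discontinuation was intended, extending the approval sentence would permit what the sponsor meant to forbid.

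A second objection is oversight. Section 7.2.2 requires serious laboratory abnormalities to reach the principal investigator, the coordinating group and the drug supplier within one working day, and Section 12.2 provides monthly safety review. A Grade 4 elevation would often qualify as serious, so the decision would often be visible to others. That stands, but a report is not an approval.

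A reader might also infer a material liver hazard from restarting at 68 mcg, given that 73 mcg was not tolerated in dose finding. The documents do not support that step. The bar on reductions from 68 mcg applies equally to Grade 3, and 73 mcg is not used here. Section 5.1.2 reports that the 73 mcg events were reversible, with the affected patients remaining on treatment, and that 6 patients at 68 mcg had no significant liver-enzyme elevations. Section 7.3.3 reports that most Grade 3 or 4 ALT/AST elevations improved to Grade 1 or less within 7 days and that more than 90% of patients could continue beyond their worst-grade elevation. These data are reassuring about restart. They also show that restart is a decision sites will face.

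**Conclusion.** The point holds as a minor defect in a stated safety rule. As written, the combined row requires written approval to restart after Grade 3, and neither approval nor discontinuation after Grade 4. No other text supplies either for a Grade 4 elevation outside Grade 3 or 4 CRS. The likeliest explanation is a drafting slip, since the same wording leaves no gap in the CRS section, but the document cannot prove the origin.

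At most about 0.4 such elevations are expected in 23 patients, on the assumption that the grouped 1.8% rate carries over. The affected subset may be smaller by an amount that cannot be derived. The protocol does not direct a Grade 4 restart and gives no outcome data specific to one, so no excess harm is claimed. Endpoints, sample size and analysis are unaffected.

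**What to change.** In the Grade 3 or 4 liver-enzyme row of Appendix B, insert the words *or 4* after *Grade 3* in the approval sentence, so that restart after either grade needs discussion with, and written approval from, the Medical Monitor. This matches the protocol's own policy of Medical Monitor agreement for other Grade 3 or 4 events. If the sponsor instead intended Grade 4 to end treatment, as it does for CRS, split the row and state permanent discontinuation at Grade 4. The sponsor should confirm which was meant before amending.

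The first option costs a two-word change and, under the stated assumption, at most about 0.4 extra Medical Monitor contacts over the trial. The second would end treatment for a patient who might have resumed, which is why it should be adopted only if it was the intent.
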